#### 9.3.2.1 Serum for PD Measurements

Serial blood samples (one 5-mL sample per scheduled time) for PD analysis will be collected according to Table 9.e. In addition, serum prolactin level will be measured in a laboratory test at Screening for safety assessment by local laboratory.

## Table 9.e Collection of Blood Samples for PD Analysis

Analyte	Matrix	Study Day	Scheduled Time	
Prolactin	Serum	1-2	Predose, 1, 2, 4, 6, and 24 hours post single dose	
Prolactin	Serum	3-6	Just before morning dose	
Prolactin	Serum	7-8	Predose, 1, 2, 4, 6, and 24 hours post morning dose	
Prolactin	Serum	14	-	

## 9.3.2.2 Bioanalytical Methods

Serum prolactin levels for PD analysis will be measured using an in vitro diagnostic assay

9.3.3.2

Not applicable.

## 9.3.4 Confinement

In either Cohort 1, 2, or 3, each subject will be confined from Day -1 to the morning of Day 8 and discharged after the investigator's or sub-investigator's confirmation of no significant abnormality in his health through physical examination and tests on Day 8, at 24-hour post morning dose of Day 7.

## **10.0 ADVERSE EVENTS**

## **10.1 Definitions and Elements of AEs**

An AE is defined as any untoward medical occurrence in a clinical investigation subject who has signed informed consent to participate in a study; it does not necessarily have to have a causal relationship with the treatment or study participation.

An AE can therefore be any unfavorable and unintended sign (eg, a clinically significant abnormal laboratory finding), symptom, or disease temporally associated with the study participation, whether or not it is considered related to the drug or study procedure.

An untoward finding generally may:

- Indicate a new diagnosis or unexpected worsening of a preexisting condition. (Intermittent events for pre-existing conditions or underlying disease should not be considered AEs.)
- Necessitate therapeutic intervention.
- Require an invasive diagnostic procedure.
- Require discontinuation or a change in dose of study medication or a concomitant medication.
- Be considered unfavorable by the investigator or sub-investigator for any reason.

Diagnoses versus signs and symptoms:

• Each event should be recorded to represent a single diagnosis. Accompanying signs (including abnormal laboratory values or ECG findings) or symptoms should NOT be recorded as additional AEs. If a diagnosis is unknown, sign(s) or symptom(s) should be recorded appropriately as an AE(s).

Laboratory values and ECG findings:

- Changes in laboratory values or ECG parameters maybe considered AEs if they are judged to be clinically significant (ie, if some action or intervention is required or if the investigator or sub-investigator judges the change to be beyond the range of normal physiologic fluctuation). A laboratory re-test and/or continued monitoring of an abnormal value are not considered an intervention. In addition, repeated or additional noninvasive testing for verification, evaluation or monitoring of an abnormality is not considered an intervention.
- If abnormal laboratory values or ECG findings are the result of pathology for which there is an overall diagnosis (eg, increased creatinine in renal failure), the diagnosis only should be reported appropriately as an AE.

Pre-existing conditions:

• A pre-existing condition (present at the time of signing of informed consent) is considered a concurrent medical condition and should NOT be recorded as an AE. A baseline evaluation (eg, laboratory test, ECG, X-ray, etc) should NOT be recorded as an AE unless related to a study procedure. However, if the subject experiences a worsening or complication of such a

TAK-906	
Study ID TAK-906-1004	Page 46 of 71
Protocol	6 June 2017

concurrent medical condition, the worsening or complication should be recorded appropriately as an AE (worsening or complication occurs after informed consent is signed). The investigator or sub-investigator should ensure that the event term recorded captures the change in the condition (eg, "worsening of...").

- If a subject has a pre-existing episodic condition (eg, asthma, epilepsy), any occurrence of an episode should only be captured as an AE if the episodes become more frequent, serious, or severe in nature, that is, the investigator or sub-investigator should ensure that the AE term recorded captures the change from baseline in the condition (eg, "worsening of...").
- If a subject has a degenerative concurrent condition (eg, cataracts, rheumatoid arthritis), worsening of the condition should only be captured as an AE if occurring to a greater extent to that which would be expected. Again, the investigator or sub-investigator should ensure that the AE term recorded captures the change in the condition (eg, "worsening of...").

Worsening of AEs:

• If the subject experiences a worsening or complication of an AE after the first administration of study medication or after any change in study medication, the worsening or complication should be recorded as a new AE. The investigator of sub-investigator should ensure that the AE term recorded captures the change in the condition (eg, "worsening of...").

Changes in severity of AEs:

• If the subject experiences a change in the severity of an AE that is not associated with a change in study medication, the event should be captured once with the maximum severity recorded.

Preplanned surgeries or procedures:

• Preplanned procedures (surgeries or therapies) that were scheduled prior to signing of informed consent are not considered AEs. However, if a preplanned procedure is performed early (eg, as an emergency) due to a worsening of the pre-existing condition, the worsening of the condition should be captured appropriately as an AE. Complications resulting from any planned surgery should be reported as AEs.

Elective surgeries or procedures:

• Elective procedures performed where there is no change in the subject's medical condition should not be recorded as AEs but should be documented in the subject's source documents. Complications resulting from an elective surgery should be reported as AEs.

Overdose:

- An overdose is defined as a known deliberate or accidental administration of investigational drug, to or by a study subject, at a dose above that which is assigned to that individual subject according to the study protocol. It is up to the investigator or the reporting physician to decide whether a dose is to be considered an overdose, in consultation with the Sponsor.
- All cases of overdose (with or without associated AEs) will be documented on an Overdose page of the eCRF, in order to capture this important safety information consistently in the

database. AEs associated with an overdose will be documented on AE CRF(s) according to Section 10.0.

- Serious adverse events (SAEs) of overdose should be reported according to the procedure outlined in Section 10.2.9.
- In the event of drug overdose, the subject should be treated symptomatically.

# 10.1.1 SAEs

An SAE is defined as any untoward medical occurrence that:

- 1. Results in DEATH.
- 2. Is LIFE THREATENING.
  - The term "life threatening" refers to an event in which the subject was at risk of death at the time of the event; it does not refer to an event that hypothetically might have caused death if it were more severe.
- 3. Requires inpatient HOSPITALIZATION or prolongation of existing hospitalization.
- 4. Results in persistent or significant DISABILITY/INCAPACITY.
- 5. Is a CONGENITAL ANOMALY/BIRTH DEFECT.
- 6. Is an IMPORTANT MEDICAL EVENT that satisfies any of the following:
  - May require intervention to prevent items 1 through 5 above.
  - May expose the subject to danger, even though the event is not immediately life threatening or fatal or does not result in hospitalization.
  - Includes any event or synonym described in the Takeda Medically Significant AE List (Table 10.a).

Term		
Acute respiratory failure/acute respiratory	Hepatic necrosis	
distress syndrome	Acute liver failure	
Torsade de pointes/ventricular fibrillation/	Anaphylactic shock	
ventricular tachycardia	Acute renal failure	
Malignant hypertension	Pulmonary hypertension	
Convulsive seizures	Pulmonary fibrosis	
Agranulocytosis	Confirmed or suspected endotoxin shock	
Aplastic anemia	Confirmed or suspected transmission of infectious agent by	
Toxic epidermal necrolysis/	a medicinal product	
Stevens-Johnson syndrome	Neuroleptic malignant syndrome/malignant hyperthermia	
	Spontaneous abortion/stillbirth and fetal death	

## Table 10.a Takeda Medically Significant AE List

Note: Terms identified on the Medically Significant AE List represent the broad medical concepts to be considered as "Important Medical Events" satisfying SAE reporting requirements.

#### **10.2 AE Procedures**

#### 10.2.1 Assigning Severity/Intensity of AEs

The different categories of severity/intensity are:

Mild:	The event is transient and easily tolerated by the subject.
Moderate:	The event causes the subject discomfort and interrupts the subject's usual activities.
Severe:	The event causes considerable interference with the subject's usual activities.

#### **10.2.2** Assigning Causality of AEs

The relationship of each AE to study medication(s) will be assessed using the following categories:

- Related: An AE that follows a reasonable temporal sequence from administration of a drug (including the course after withdrawal of the drug), or for which a causal relationship is at least a reasonable possibility, ie, the relationship cannot be ruled out, although factors other than the drug, such as underlying diseases, complications, concomitant drugs and concurrent treatments, may also be responsible.
  Not Related: An AE that does not follow a reasonable temporal sequence from administration
- Not Related: An AE that does not follow a reasonable temporal sequence from administration of a drug and/or that can reasonably be explained by other factors, such as underlying diseases, complications, concomitant medications and concurrent treatments.

## **10.2.3** Assigning Causality of AEs to Study Procedures

The causality of each AE to study procedures will be assessed.

The causality should be assessed as Related if the investigator or sub-investigator considers that there is reasonable possibility that an event is due to a study procedure. Otherwise, the causality should be assessed as Not Related.

## 10.2.4 Start Date

The start date of the AE is the date that the first signs/symptoms were noted by the subject and/or investigator.

## 10.2.5 End Date

The end date of the AE is the date at which the subject recovered, the event resolved but with sequelae or the subject died.

## 10.2.6 Pattern of Adverse Event (Frequency)

Episodic AEs (eg, headache) or those which occur repeatedly over a period of consecutive days are intermittent. All other events are continuous.

## 10.2.7 Action Taken With Study Treatment

- Drug withdrawn a study medication is stopped due to the particular AE.
- Dose not changed the particular AE did not require stopping a study medication.
- Unknown only to be used if it has not been possible to determine what action has been taken.
- Not applicable a study medication was stopped for a reason other than the particular AE eg, the study has been terminated, the subject died, dosing with study medication had not yet started or dosing with study medication was already stopped before the onset of the AE.

## 10.2.8 Outcome

- Recovered/resolved subject returned to first assessment status with respect to the AE.
- Recovering/resolving the intensity is lowered by one or more stages: the diagnosis has or signs/symptoms have almost disappeared; the abnormal laboratory value improved, but has not returned to the normal range or to the baseline value; the subject died from a cause other than the particular AE with the condition remaining "recovering/resolving."
- Not recovered/not resolved there is no change in the diagnosis, signs or symptoms; the intensity of the diagnosis, signs/symptoms or laboratory value on the last day of the observed study period has become worse than when it started; is an irreversible congenital anomaly; the subject died from another cause with the particular AE state remaining "Not recovered/not resolved."

TAK-906	
Study ID TAK-906-1004	Page 50 of 71
Protocol	6 June 2017

- Recovered/Resolved with sequelae the subject recovered from an acute AE but was left with permanent/significant impairment (eg, recovered from a cardiovascular accident but with some persisting paresis).
- Fatal an AE that is considered as the cause of death.
- Unknown the course of the AE cannot be followed up due to hospital change or residence change at the end of the subject's participation in the study.

#### 10.2.9 Collection and Reporting of AEs, SAEs, and Abnormal LFTs

#### 10.2.9.1 Collection Period

Collection of AEs (ie, AEs, SAEs, and Abnormal LFTs) will commence at the time the subject signs the informed consent. Routine collection of AEs will continue until the follow-up visit on Day 14.

#### 10.2.9.2 Reporting AEs

At each study visit, the investigator or sub-investigator will assess whether any subjective AEs have occurred. A neutral question, such as "How have you been feeling since your last visit?" may be asked. Subjects may report AEs occurring at any other time during the study. Subjects experiencing an SAE prior to the first exposure to study drug must be monitored until the symptoms subside and any clinically relevant changes in laboratory values have returned to baseline or until there is a satisfactory explanation for the changes observed. Nonserious AEs that begin prior to the first exposure to study drug, whether related or unrelated to study procedure, need not be followed-up for the purposes of the protocol.

All subjects experiencing an AE after first exposure to study drug, whether it is considered associated with use of the study medication or not, must be monitored until the symptoms subside and any clinically relevant changes in laboratory values have returned to baseline or until there is a satisfactory explanation for the changes observed. All AEs will be documented in the AE page of the eCRF, whether or not the investigator or sub-investigator concludes that the event is related to the drug treatment. The following information will be documented for each event:

- Event term.
- Start and end date and time.
- Pattern of AE (frequency).
- Severity/Intensity.
- Investigator's or sub-investigator's opinion of the causality between the event and administration of study drug(s) (related or not related).
- Investigator's or sub-investigator's opinion of the causality to study procedure(s), including the details of the suspected procedure.
- Action taken with trial drug.

- Outcome of event.
- Seriousness.
- Timing of occurrence (after administration of study drug).
- QTc prolongation associated AEs, neurologic AEs or hyperprolactinemia associated AEs, or not.

## 10.2.9.3 Reporting SAEs

When an SAE occurs through the AE collection period it should be reported according to the procedure outlined below:

An SAE should be reported by the investigator or sub-investigator to the Sponsor (see Protocol Annex 1) within 1 business day of the first onset or notification of the SAE, along with any relevant information. The investigator should submit a detailed SAE Form to the Sponsor within 10 calendar days. The information should be completed as fully as possible but contain, at a minimum:

- A short description of the event and the reason why the event is categorized as serious.
- Subject identification number.
- Investigator's or sub-investigator's name.
- Name of the study medication(s).
- Causality assessment.

Any SAE spontaneously reported to the investigator or sub-investigator following the AE collection period should be reported to the Sponsor if considered related to study participation.

## SAE Follow-Up

If information is not available at the time of the first report becomes available at a later date, the investigator or sub-investigator should complete a follow-up SAE form or provide other written documentation and submit it to the Sponsor. Copies of any relevant data from hospital notes (eg, ECGs, laboratory tests, discharge summary, postmortem results) should be submit to the Sponsor, if requested.

All SAEs should be followed up until resolution or a permanent outcome for the event.

# 10.2.9.4 Reporting QTc prolongation associated AEs, neurologic AEs, and hyperprolactinemia associated AEs

Considering the mechanism of action of TAK-906 and the safety profile of existing dopamine  $D_2/D_3$  receptor antagonists on the market, the following AEs (treatment-emergent only, serious or non-serious) are considered to be ones for which ongoing monitoring and rapid communication by the investigator to Takeda may be appropriate, and may require further investigation in order to characterize and understand in this study.

QTc prolongation associated AEs:

• Torsade de pointes, Sudden death, Ventricular tachycardia, Ventricular fibrillation and flutter, Syncope, and Seizure.

Neurologic AEs:

• Extrapyramidal disorder, Tardive dyskinesia, Akathisia, and Parkinsonian like disorder.

Hyperprolactinemia associated AEs.

• Hyperprolactinemia, Libido decreased, Sexual dysfunction, Gynecomastia, and Galactorrhoea.

If these AEs are considered to be clinically significant, it should be reported to the Sponsor immediately or within 1 business day of onset or subject's notification of the event. An AE Form specified to these AEs or an SAE Form should be completed, signed, or signed and sealed by the investigator and reported to the Sponsor within 10 business days.

The investigator should record these AEs as AEs in the eCRF, and submit the original copy of the AE Form or the SAE Form along with all other required documentation to the Sponsor.

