Currently in the US, there exists a large unmet medical need because there are no approved therapies for the chronic treatment of diabetic gastroparesis. Metoclopramide, a dopamine  $D_2$  receptor antagonist, and domperidone, a peripherally-acting dopamine  $D_2/D_3$  receptor antagonist, are prokinetic agents marketed in Japan. They are known to cause extrapyramidal symptoms (EPS) and cardiovascular side effects, respectively. The most notable toxicities of metoclopramide are a category of movement disorders known as EPS [7]. EPS are caused by blockade of dopamine  $D_2$  receptors in the dorsal striatum and thus are potential side effects of all centrally-penetrant drugs that share this mechanism of action, particularly selective dopamine  $D_2$  receptor antagonists. Of greatest concern is tardive dyskinesia, a severe and often irreversible EPS. The risk of developing tardive dyskinesia increases with dose level and duration of treatment and as such, the US package insert includes a black box warning regarding the chronic use of metoclopramide for longer than 12 weeks. Domperidone is a peripherally-acting dopamine  $D_2/D_3$  receptor antagonist

TAK-906	
Study ID TAK-906-1004	Page 14 of 71
Protocol	6 June 2017

marketed for use as an antiemetic and prokinetic agent in a number of countries worldwide including Japan, although not in the US due to its cardiovascular safety profile which includes risks for drug-induced long QT syndrome, torsades de pointes, and sudden cardiac death [8].

Nonclinical in vitro and in vivo pharmacology studies have demonstrated that TAK-906 has  $D_2/D_3$  antagonism with a potency comparable to or greater than domperidone and metoclopramide. TAK-906 does not readily penetrate the blood brain barrier (BBB) and therefore it can block dopamine  $D_2/D_3$  receptors in the area postrema outside of the BBB to reduce symptoms of gastroparesis, such as nausea and vomiting, but not block those inside of the BBB which are likely to cause EPS [9][10]. In addition, TAK-906 is a very weak inhibitor of the human ether-a-go-go related gene (hERG) channel, thus reducing the potential for fatal arrhythmias [8]. Therefore, TAK-906 is expected to exhibit comparable or greater prokinetic effects and less adverse effects compared with existing products on the market, which makes TAK-906 a promising drug for the treatment of gastroparesis.

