# 5.2.3 Trial Exploratory Objectives

# 5.3 Endpoints

# 5.3.1 Primary Endpoint

The study's primary endpoints of safety and tolerability will be assessed through TEAEs including QTc prolongation associated AE, neurologic AE, and hyperprolactinemia associated AE, physical examinations, vital signs, clinical laboratory tests, and 12-lead electrocardiogram (ECG).

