# 6.3.2 Rationale for Dose

The proposed starting dose is 50 mg BID and the proposed highest dose is 100 mg BID. Several considerations were given in selecting these doses: safety,

highest dose is 100 mg BID. Several considerations were given in selecting these doses: safety, tolerability, PK and PD (serum prolactin concentration).

Based on the overall nonclinical safety profile, the dog was considered the most sensitive species for TAK-906 and was used as the basis for the maximum recommended starting dose (MRSD) in the foreign phase 1 study. The TAK-906 maleate no-observed-adverse-effect level (NOAEL) in the pivotal 28-day repeat-dose study in dogs was 50 mg/kg/day, at which central nervous system (CNS)-associated pharmacological effects typical of this pharmacologic class occurred on multiple occasions in all animals, including mild sedation, mild intermittent and/or continuous tremors and ataxia. The lowest observed effect level (LOEL) for CNS effects in the dog was considered to be 10 mg/kg/day. At 1 mg/kg/day of TAK-906 mateate, a single occurrence of mild tremors was observed in 1 female dog on Day 1 and thus a 1 mg was considered an appropriately conservative dose at which to establish MRSD. The MRSD of 0.06 mg/kg/day (3.6 mg/day per 60 kg person) was calculated based on human equivalent dose converted using body surfice area and safety factor (10). Based on the results, a dose of 5 mg is considered as an safe initial clinical dose. In the foreign phase 1 study, single dose ranging from 5 to 300 mg and multiple doses of 50 and 100 mg BID for 5 days were examined. From the results, favorable safety and tolerability of TAK-906 in non-Japanese subjects was demonstrated within the range of doses studied. The proposed starting dose for this study is 50 mg BID

At a dose of 50 mg BID at steady state (AUC24 116 h\*ng/mL; Cmax 31.2 ng/mL), AUC and Cmax exposure margins at the dog LOEL for CNS effects are  $\geq$ 3-fold and  $\geq$ 8-fold, respectively.

The proposed highest dose for this study is 100 mg BID

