7.11.1.4 Displays of Treatment-Emergent Adverse Events

Analysis Set:	Safety Analysis Set			
Analysis Variables:	TEAE			
Categories:	Intensity [Mild, Moderate, Severe]			
Analytical Methods:	The following summaries will be provided using frequency distribution by dose.			
	TEAEs will be coded using the MedDRA and will be summarized using SOC and PT. SOC			
	will be sorted alphabetically and PT will be sorted in decreasing frequency for tables provided			
	by SOC and PT. SOC and PT will be sorted in decreasing frequency for tables provided by			
	SOC only or PT only.			
	(1) Treatment-Emergent Adverse Events by System Organ Class and Preferred Term			
	(2) Treatment-Emergent Adverse Events by System Organ Class			
	(3) Treatment-Emergent Adverse Events by Preferred Term			
	(4) Drug-Related Treatment-Emergent Adverse Events by System Organ Class and Preferred Term			
	(5) Intensity of Treatment-Emergent Adverse Events by System Organ Class and Preferred			
	Term			
	(6) Intensity of Drug-Related Treatment-Emergent Adverse Events by System Organ Class, and Preferred Term			
	CONFIDENTIAL			

Number of events

- (7) Treatment-Emergent Adverse Events Leading to Study Drug Discontinuation by System Organ Class and Preferred Term
- (8) Serious Treatment-Emergent Adverse Events by System Organ Class and Preferred Term
- (9) QTc prolongation associated Treatment-Emergent Adverse Events by System Organ Class and Preferred Term
- (10) Neurologic Treatment-Emergent Adverse Events by System Organ Class and Preferred Term
- (11) Hyperprolactinemia associated Treatment-Emergent Adverse Events by System Organ Class and Preferred Term
- (12) Drug-Related QTc prolongation associated Treatment-Emergent Adverse Events by System Organ Class and Preferred Term
- (13) Drug-Related Neurologic Treatment-Emergent Adverse Events by System Organ Class and Preferred Term
- (14) Drug-Related Hyperprolactinemia associated Treatment-Emergent Adverse Events by System Organ Class and Preferred Term

The frequency distribution will be provided according to the rules below. Number of subjects

- Summary tables other than (5), and (6) A subject with multiple occurrences of TEAE within a SOC will be counted only once in that SOC. A subject with multiple occurrences of TEAE within a PT will be counted only once in that PT. Percentages will be based on the number of subjects in the safety analysis set.

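### The only definition of 'neurologic AE' names four terms and none of the CNS effects reported in dogs, so the dedicated neurologic tables, if built from it, can read zero when those effects occur

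*Protocol*

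**What the plan says.** Protocol 5.3.1 assesses safety and tolerability through "TEAEs including QTc prolongation associated AE, neurologic AE, and hyperprolactinemia associated AE", together with examinations, vital signs, laboratory tests and ECG. SAP 5.1 repeats this and adds no definition.

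The content of the neurologic group is given once, in Protocol 10.2.9.4: "Extrapyramidal disorder, Tardive dyskinesia, Akathisia, and Parkinsonian like disorder". Nothing marks these terms as examples. The stated basis is the drug's mechanism and the safety profile of marketed drugs of the class. Protocol 10.2.9.2 has the investigator record, for each event, whether it belongs to one of the three special groups. It offers no further definition.

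The SAP plans a table titled "Neurologic Treatment-Emergent Adverse Events by System Organ Class and Preferred Term" over the whole study (7.11.1.4, table 10), for the single dose period (7.11.1.5, table 9) and for the multiple dose period (7.11.1.6, table 10). Drug-related versions are tables 13, 12 and 13 of those sections. No preferred terms, MedDRA query or eCRF variable is named as the source.

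Protocol 6.3.2 describes the dog findings at 50 mg/kg/day, the no-observed-adverse-effect level (NOAEL). CNS effects that it treats as typical of the class "occurred on multiple occasions in all animals, including mild sedation, mild intermittent and/or continuous tremors and ataxia". It adds that "The lowest observed effect level (LOEL) for CNS effects in the dog was considered to be 10 mg/kg/day", and that at 1 mg/kg/day "a single occurrence of mild tremors was observed in 1 female dog on Day 1". That last finding led to the conservative dose used to derive the maximum starting dose of the foreign phase 1 study.

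**The concern.** The list is said to rest on mechanism and class profile. The protocol's own account of class-typical CNS effects of this compound consists of three effects that the list does not name. A summary called neurologic, attached to the primary endpoint, would be expected to gather them.

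What is at stake is how a zero is read. Protocol 4.1 and 4.2 argue that the drug crosses the blood-brain barrier poorly and should therefore cause fewer extrapyramidal effects. An empty neurologic table could be cited in support of that argument while subjects with tremor, ataxia or sedation sit in other rows of other tables.

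**Working it through.** No stated statistical figure is in dispute, and the sample size is not based on power. The check is mainly a comparison of passages.

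**Step 1: dog effects against the list.**

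| Effect in dogs (Protocol 6.3.2) | Named in 10.2.9.4? | Could it be placed under a listed term? |
|---|---|---|
| Tremor | No | Possibly, if judged extrapyramidal or parkinsonian |
| Ataxia | No | No listed term fits readily |
| Sedation | No | No listed term fits readily |

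**Step 2: how an isolated sign is recorded.** Protocol 10.1 has a sign or symptom recorded as the event when no diagnosis is known. An isolated tremor would therefore enter the database as tremor. Whether it is then classed as neurologic is left to judgement.

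**Step 3: what the tables would count.** The SAP leaves three constructions open.
- Built from the four terms: events recorded as tremor, ataxia or sedation contribute nothing.
- Built from the eCRF classification: the count depends on how the investigator reads 10.2.9.4, the only guide in the documents.
- Built from a MedDRA grouping: the events might be included, but no grouping is named.

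**Step 4: size.** There are 3 cohorts of 6 active and 2 placebo subjects: 3 × 8 = 24, made up of 18 active and 6 placebo, as the plan states. One subject left out of a dose group is 1/6 = 16.7 percentage points. The chance of at least one case among n subjects with true rate p is 1 − (1 − p)^n. The documents give no rate, so the values of p below are assumptions.

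| Assumed p | n = 6 (one dose) | n = 18 (all active) |
|---|---|---|
| 10% | 1 − 0.9^6 = 47% | 85% |
| 20% | 1 − 0.8^6 = 74% | 98% |
| 30% | 1 − 0.7^6 = 88% | 99.8% |

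Under the first construction the neurologic table would count none of these cases.

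**Step 5: what the list can detect in this trial.** Dosing covers Day 1 and Days 3 to 7, which is 1 + 5 = 6 days. Writing about metoclopramide, Protocol 4.1 says that "The risk of developing tardive dyskinesia increases with dose level and duration of treatment". One of the four listed terms is therefore unlikely to appear here, although not impossible.

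**Step 6: where the events would still be seen.** SAP 7.11.1.4 to 7.11.1.6, tables 1 to 6, cover all treatment-emergent events by system organ class and preferred term, by relatedness and by intensity. Protocol 11.1.5.1 lists every such event. Protocol 6.2 puts all Cohort 1 adverse events before the investigator, blinded, prior to Cohort 2.

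**The case against.** The strongest reply is that the primary endpoint covers all treatment-emergent events and the three special groups are only subsets. With six active subjects per dose, a single tremor is easy to find in the general tables. This stands, and it limits the point to the dedicated summary.

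Second, the four entries may be broad concepts rather than preferred terms. Protocol 4.1 describes extrapyramidal symptoms as a class of movement disorders, so a drug-related tremor could be placed there. The SAP also never says that the list determines its tables. Both statements are correct, which is why the conclusion is conditional. They do not dispose of it: sedation and ataxia fit none of the four terms well, and an unstated selection rule is itself the gap.

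Third, the list follows the marketed-class toxicity that Protocol 4.1 stresses, and sedation is non-specific. That is a fair reason for keeping a narrow group. It is not a reason for having no broader one when 6.3.2 calls the other effects class-typical.

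Fourth, the dog effects were mild and occurred at the NOAEL, and the foreign phase 1 study is reported as well tolerated at 50 and 100 mg BID. Some of that study's results are absent from the public text, and they may explain the choice of terms. This lowers the expected number of events but leaves the definition unchanged.

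**Conclusion.** The point holds in a limited form. The sole definition of a named component of the primary endpoint omits three CNS effects that the same protocol calls typical of the class, and the SAP supplies no other selection rule. If the six neurologic tables are built from the four terms, they can read zero when those effects occur, at 16.7 percentage points per uncounted subject in a dose group. This rests on two assumptions: that the tables or the eCRF classification follow 10.2.9.4, and that isolated signs are recorded under their own names as 10.1 directs.

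Three stronger readings are tempting and are not supported.
- A reader might infer that the primary endpoint is blind to these events. It is not, because every treatment-emergent event is tabulated and listed.
- A reader might infer that such events escape needed rapid reporting. Under 10.2.9.4 the one-business-day rule applies only to events judged clinically significant, and serious events follow their own route whatever the list says.
- A reader might infer that the exposure margins make CNS effects likely. The margin to the dog CNS effect level at 50 mg BID is stated only as lower bounds, at least 3-fold for AUC and 8-fold for Cmax. The figures for 100 mg BID are relative to the NOAEL and reproduce: 5880/(2 × 200.5) = 14.7 against about 15, and 1900/71.6 = 26.5 against about 27. Scaling the AUC bound to 100 mg BID gives (3 × 116)/401 = 0.87. That is a scaled lower bound, not an estimated margin, and it predicts nothing about event rates.

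**What to change.** Before unblinding, state the selection rule in SAP 7.11.1.4 (tables 10 and 13), 7.11.1.5 (tables 9 and 12) and 7.11.1.6 (tables 10 and 13). Show neurologic events in two groups, by dose beside pooled placebo:
- **Narrow:** the current four terms.
- **Broad:** the narrow group plus the preferred terms for tremor, ataxia/coordination disturbance and sedation/somnolence.

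Align the eCRF classification guidance with this rule. The sponsor should reconcile the list in Protocol 10.2.9.4 with the findings in 6.3.2, or record why they differ. Whether the rapid-reporting route extends to the added terms is for the sponsor to decide.

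The cost is wording in the SAP and the eCRF guidance, plus reconciliation of one protocol section. No new visit, sample or subject is needed. The small downside is that sedation is non-specific, and showing the two groups separately deals with that.
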